### Revision history:

Revision no	Date	Description
0	09MAR2022	First version
1	15MAR2022	Updated with clarification of study flow and minor corrections throughout the document

## STATEMENT OF COMPLIANCE

This study will be performed in consistency with applicable parts of the current versions of the Declaration of Helsinki, ISO 14155, Regulation (EU) 2017/745 (MDR) and applicable regional or national regulatory requirements as well as any additional requirements imposed by Institutional Review boards and Ethical committees.

**Referenced documents:**

- [A] Doc-00064573 Intended purpose Ponto bone anchored hearing system (BAHS)
- [B] Doc-00069507 PMCF plan for Ponto sound processors and accessories
- [C] Doc-00065550 Medical background Oticon Medical BAHS

**Appendix:**

1. Part number for devices included in the study
2. The International Outcome Inventory of Hearing Aids (IOI-HA)

## 1 SYNOPSIS

Clinical Study Title	Cross-sectional evaluation of the subjective performance and satisfaction with Oticon Medical's Ponto Sound Processors
Study Code	BC112
Device (s)	Ponto Sound Processors
Principal investigator(s):	NA Study carried out by sponsor through online survey
Sponsor:	Oticon Medical AB [name]
Methodology:	Observational Cross-sectional online survey
Inclusion/exclusion criteria:	Inclusion: 

• Online consent form filled out

• Has been fitted with a Ponto Sound Processor

Objective(s):	Primary Objective 

• Evaluate subjectively assessed overall hearing performance and satisfaction with the Oticon Medical's Ponto sound processors.

 Secondary Objective (s) 

• Evaluate subjectively assessed hearing performance and satisfaction with the Oticon Medical's Ponto sound processors.

• Evaluate non-usage among patients fitted with a Ponto sound processor

Endpoints	Primary Endpoint 

• Overall IOI-HA score

 Secondary Endpoint(s) 

• Factor 1, Factor 2 IOI-HA and per item IOI-HA score (Ponto 4 and Ponto 5 Mini)

• Percentage of users fitted with a Ponto sound processor that have stopped using the Ponto sound processor and is unaided

Duration of study period:	10 months
Number of Participants	1000
Study plan prepared by:	[name], Clinical Trial Manager, Oticon Medical AB

### 3 LIST OF ABBREVIATIONS

AE	Adverse Event
BAHS	Bone Anchored Hearing System
BC	Bone conduction
CE	Conformité Européenne
CHL	Conductive Hearing Loss
CIP	Clinical Investigation Plan
dB	Decibel
EDC	Electronic Data Capture
FDA	Food and Drug Administration
GCP	Good Clinical Practice
GDPR	General Data Protection Regulation
HIPAA	Health Insurance Portability and Accountability Act
IRB	Institutional Review Board
IOI-HA	International Outcome Inventory for Hearing Aids
ISO	International Organization for Standardization
MDR	Medical Device Regulation
MHL	Mixed Hearing loss
OM	Oticon Medical
PMCF	Post Market Clinical Follow-up
PTA	Pure Tone Average
No	Number
SAE	Severe Adverse Event
SP	Sound Processor
SSD	Single Sided Deafness
US	United States

## 4 INTRODUCTION

Bone conduction hearing systems use the body's natural ability to transfer sound through bone conduction. The bone conduction system picks up sound and converts it into vibrations that are transferred through the skull bone to the inner ear(s) (cochlea). A bone conduction system transmits sound directly to the cochlea independently of the function of the ear canal and middle ear. Thus, for patients with conductive hearing losses (CHL) or mixed hearing losses (MHL), patients with lasting hearing loss following a middle ear disease (such as for instance chronic otitis media, cholesteatoma, otosclerosis or other ossicular diseases) or malformations (such as aural atresia and/or microtia), one utilizes that the vibrations are bypassing the conductive impairment in the ear canal or middle ear, stimulating the cochlea directly. For single-sided deaf (SSD) Participants, one utilizes that the vibrations are transmitted in the same manner via the skull bone to the (functioning) cochlea on the contralateral side [1].

[figure not shown]
Bone Anchored Hearing Systems (BAHS) have been used since the late 1970's and are divided into two types: direct drive and skin drive, both having two sub-types (see Figure 1). Direct drive denotes systems where the vibrations are transmitted directly to the bone (e.g. through an abutment connected to an osseointegrated implant), while in skin drive solution there is a layer of soft tissue between the transducer and the bone (e.g. when utilizing a Softband). Percutaneous direct drive, also referred to as BAHS, is the most common type with more than 150.000 users world-wide [1].

**Figure 1** Classification of bone conduction systems

### 4.1 The Ponto System

The Ponto system is an osseointegrated, percutaneous (direct drive) bone conduction system, which replaces the function of the outer and middle ear. This replacement happens by providing mechanical energy to the cochlea from a transducer in the sound processor and via a percutaneous implant anchored in the temporal bone. Sound is picked up by the microphones in the external sound processor and converted to mechanical energy (vibrations) by the transducer in the sound processor and is then transmitted to a skin-penetrating abutment which is connected to the implant in the temporal bone of the skull (see Figure 2). The vibrations are conveyed from the implant by means of bone conduction to the cochlea. In the cochlea, the vibrations are converted to signals that are transmitted to the brain through the auditory nerve.

**Figure 2 Ponto sound processor connected to an abutment**

## 5 DESCRIPTION OF THE DEVICE

The devices investigated in the study will be the Ponto sound processors. Ponto sound processors are non-sterile devices containing a coupling, an electromagnetic transducer (vibrator), microphones, sound processor electronics and signal processing chip. The sound processors are powered by a zinc air hearing aid batteries accessible through a battery drawer. The Ponto sound processor are fitted and adapted to the patient's by a hearing care professional using a computer with a fitting software (Genie Medical) developed together with the sound processors.

### 5.1 Identification of the Device

The subjects included will have been fitted with a Ponto sound processor and they will evaluate the sound processor that they are currently fitted with. The study will focus on devices from the following Ponto families:

- Ponto
- Ponto Pro and Ponto Pro Power
- Ponto Plus and Ponto Plus Power
- Ponto 3, Ponto 3 Power and Ponto 3 SuperPower
- Ponto 4
- Ponto 5 Mini and Ponto 5 SuperPower

The Ponto sound processor comes in a range of different colors. Part number for each style and color that can be included in the study is listed in Appendix 1.

### 5.2 Manufacturer

The Ponto sound processors are manufactured by Oticon Medical AB, Askim, Sweden. Oticon Medical AB is ISO 13485 certified and has CE-marked and FDA-cleared products for hearing healthcare on the market.

### 5.3 Intended Purpose

The Ponto sound processors are intended for improvement of hearing for patients with conductive or mixed hearing losses, whether unilaterally or bilaterally fitted, or for those with single sided deafness[A].

### 5.4 Population and indications [A]

The study will include subjects that has been fitted with a Ponto Sound Processor. The Ponto system is

intended for the following patients and indications:

- Patients with conductive or mixed hearing losses, who can still benefit from amplification of the sound. The pure tone average (PTA) bone conduction (BC) threshold (measured at 0.5, 1, 2 and 3 kHz) of the indicated ear should be better than or equal to 45 dB HL for use with the Ponto, Ponto Pro, Ponto Plus, Ponto 3, Ponto 4 and Ponto 5 Mini sound processors, 55 dB HL for use with the Ponto Pro Power, Ponto Plus Power and Ponto 3 Power sound processors and 65 dB HL for use with the Ponto 3 SuperPower and Ponto 5 SuperPower sound processors.
- Bilateral fitting is applicable for most patients having a symmetrically conductive or mixed hearing loss. The difference between the left and right sides' BC thresholds should be less than 10 dB on average measured at 0.5, 1, 2 and 4 kHz, or less than 15 dB at individual frequencies.
- Patients who have a profound sensorineural hearing loss in one ear and normal hearing in the opposite ear (i.e. single sided deafness or "SSD"). The pure tone average (PTA) air conduction (AC) threshold of the hearing ear should then be better than or equal to 20 dB HL (measured at 0.5, 1, 2 and 3 kHz).
- Also indicated for any patient who is indicated for an air-conduction contralateral routing of signals (AC CROS) hearing aid, but who for some reason cannot or will not use an AC CROS.

## 6 JUSTIFICATION FOR THE DESIGN OF THE STUDY

The study is a non-interventional, observational, cross-sectional, study on users of Ponto sound processors. The purpose of this study is to evaluate subjectively assessed hearing performance and satisfaction with Oticon Medical's sound processors fitted with the Genie Medical fitting software.

The overall study purpose aims to study long-term use of Oticon Medical's sound processor Ponto (fitted with the Genie Medical fitting software) and how it impacts patient reported hearing improvements and quality of life.

The study is making use of subjective self-reported outcomes to evaluate hearing performance. Subjectively self-reported outcomes are commonly used to quantify how the patients subjectively perceive the device in their everyday life [C] and is considered to provide representative measurements of hearing improvement [2] One such subjectively self-reported outcome measure is the IOI-HA [3]. The IOI-HA contains generally applicable items for self-assessment of hearing aid fitting outcomes. It covers a minimal set of seven core outcome items targeting a different outcome domain. The domains are: daily use, benefit, residual activity limitations, satisfaction, residual participation restrictions, impact on others and quality of life. Each item has five response choices proceeding from the worst outcome to the best outcome. In terms of construction and wording, the items of the IOI-HA have been designed to be easy to read and understand. In addition it is designed to be self-explanatory and without any need for formal instructions [3]. The IOI-HA was originally designed to be distributed in paper form, but Thorén, Andersson and Lunner [4] found that the questionnaire can be distributed also in an online format without compromising reliability of the outcome. Based on the short self-explanatory design [3] together with data supporting the use of the questionnaire for online use [4] the IOI-HA has been chosen to be the questionnaire used in this study.

## 7 POTENTIAL BENEFITS AND RISKS OF THE STUDY

No additional treatments or procedures will be utilized for this study, although participants will be asked to complete a survey. Therefore, only risks associated to data capture and data privacy have been identified and these are mitigated by strict data management procedures (see Section12).

Although participants included in this study might not receive any benefit from the study, the study will promote a better understanding of satisfaction of the Ponto Sound Processors which will be shared within the field of BAHS and may lead more efficient BAHS for others. Prior to enrollment into the study the participants will receive information about potential benefits and risks. Electronically signed consent based on this information will be required from all participants prior to collecting any study specific data.

## 8 OBJECTIVES AND HYPOTHESES

The purpose of this study is to evaluate subjectively assessed hearing performance and satisfaction with Oticon Medical's Ponto sound processors (fitted with the Genie Medical fitting software).

### 8.1 Primary objective

Primary objective	Corresponding primary endpoint/outcome variable(s)	Section
A. Evaluate the subjectively assessed overall performance and satisfaction with Oticon Medical's Ponto sound processors	1. Overall IOI-HA score	9.2.1.2

### 8.2 Secondary Objective(s)

Secondary objective(s)	Corresponding primary endpoint/outcome variable(s)	Section
A. Evaluate the subjectively assessed performance and satisfaction with Oticon Medical's Ponto sound processors	1. Factor 1 IOI-HA score 2. Factor 2 IOI-HA score 3. Per item IOI-HA score	9.2.1.2
B. Evaluate non-usage among patients fitted with a Ponto sound processor	1. Percentage of users fitted with a Ponto sound processor that have stopped using the Ponto sound processor and is unaided	
C. Evaluate Ponto sound processor upgrade rate	1. Percentage of users who have been refitted with a Ponto sound processor	

## 9 DESIGN OF THE STUDY

This is a non-interventional, observational, cross-sectional, study on subjects fitted with Ponto sound processors. Subjects fitted with one or two Ponto sound processors will be invited to participate in an online survey. The survey contains questions about the subjectively experienced performance and satisfaction of the device. The survey can be filled out on computer, tablet or mobile phone and should take the participants about 10 minutes to fill out.

## 9.1 Subjects

The population for this study will be users of Ponto Sound Processors in the US. User who are a part of Oticon Medical's US user database where the users are signing up in relation to being fitted with a Ponto Sound Processor will be approached through email out-reach. When signing up for the database the users give their consent for being contacted by Oticon Medical. In addition, out-reach through social media and Oticon Medical US website will be considered to increase numbers of subjects. In all both cases, study awareness and enrollment of the participants for this study will occur after being fitted with one or two Ponto sound processor.

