### 9.1.1 *Inclusion criteria*

Following users will be included in the study:

- Online consent form filled out
- Has been fitted with at least one Ponto Sound Processor

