### 9.2.1.1 Part 1 Overall information

Following overall information will be gathered from the participants:

- Gender
- Age
- Usage of device
- Unilateral or bilateral user
- Softband or Abutment fitting
- Time of fitting (for how long they have used the device)

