## Appendix 2 The International Outcome Inventory of hearing aids

INTERNATIONAL OUTCOME INVENTORY – HEARING AIDS  
(IOI-HA)

1. Think about how much you used your present hearing aid(s) over the past two weeks. On an average day, how many hours did you use the hearing aid(s)?

none	less than 1 hours a day	1 to 4 hours a day	4 to 8 hours a day	more than 8 hours a day
				

2. Think about the situation where you most wanted to hear better, before you got your present hearing aid(s). Over the past two weeks, how much has the hearing aid helped in that situation?

helped not at all	helped slightly	helped moderately	helped quite a lot	helped very much
				

3. Think again about the situation where you most wanted to hear better. When you use your present hearing aid(s), how much difficulty do you **STILL** have in that situation?

very much difficulty	quite a lot of difficulty	moderate difficulty	slight difficulty	no difficulty
				

4. Considering everything, do you think your present hearing aid(s) is worth the trouble?

not at all worth it	slightly worth it	moderately worth it	quite a lot worth it	very much worth it
				

5. Over the past two weeks, with your present hearing aid(s), how much have your hearing difficulties affected the things you can do?

affected very much	affected quite a lot	affected moderately	affected slightly	affected not at all
				

6. Over the past two weeks, with your present hearing aid(s), how much do you think other people were bothered by your hearing difficulties?

bothered very much	bothered quite a lot	bothered moderately	bothered slightly	bothered not at all
				

7. Considering everything, how much has your present hearing aid(s) changed your enjoyment of life?

worse	no change	slightly better	quite a lot better	very much better

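### Four of the seven IOI-HA items ask about the past two weeks, but no minimum time since fitting is set, so users whose current processor does not span that window can enter the scores

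*Combined protocol and SAP*

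**What the plan says.** **The instrument (Appendix 2).** Four items carry a two-week window:
- Item 1, daily use: "Think about how much you used your present hearing aid(s) over the past two weeks".
- Item 2, benefit: "Over the past two weeks, how much has the hearing aid helped in that situation".
- Item 5, participation: "Over the past two weeks, with your present hearing aid(s), how much have your hearing difficulties affected the things you can do".
- Item 6, impact on others: "Over the past two weeks, with your present hearing aid(s), how much do you think other people were bothered by your hearing difficulties".

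Items 3, 4 and 7 state no window.

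**Who may answer.** Section 9.1.1 asks for online consent and one device condition: "Has been fitted with at least one Ponto Sound Processor". Section 9.1.2 lists no exclusions. Section 9.1 requires only that "study awareness and enrollment of the participants for this study will occur after being fitted with one or two Ponto sound processor". It describes the contact database as one "where the users are signing up in relation to being fitted with a Ponto Sound Processor". Section 11.1 says that this database is still growing, and Section 11.4 allows further outreach.

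**What is rated and recorded.** Under Section 5.1 respondents rate the processor they currently have. Section 8.2 makes refitting an outcome in its own right. Section 9.2.1.1 collects "Time of fitting (for how long they have used the device". Sections 11 to 11.4 do not use that variable, and the subgroups in Section 11.2 are by processor type only.

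**Aim.** Section 6 states that the overall purpose is to study long-term use.

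**The concern.** The primary endpoint is the Overall IOI-HA score, and four of its seven items ask the respondent to look back over 14 days with the present device. For someone fitted a few days ago, part of that window precedes the device. For someone just refitted with a newer model, part of it may belong to the previous processor. Under the all-comers rule both are eligible and fully scored.

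Two recent users with identical wear could answer item 1 differently, depending on whether they average over 14 days or only over the days since fitting. The score would then partly reflect how the question was read, or how the earlier device performed. What is at stake is the meaning of the Overall, Factor 1, Factor 2 and per-item scores for these respondents, and the fit between the sample and the long-term aim.

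**Working it through.** The plan gives no figure for this point and no power or precision calculation, so there is nothing of its own to reproduce. Everything after step 1 is illustration under stated assumptions.

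**1. Weight of the two-week items** (from Appendix 2 and the factor definitions in Section 9.2.1.2)
- Overall: items 1, 2, 5 and 6, so 4/7 = 57%.
- Factor 1 (use, benefit, satisfaction, quality of life): items 1 and 2, so 2/4 = 50%.
- Factor 2 (activity limitation, participation, impact on others): items 5 and 6, so 2/3 = 67%.

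**2. Effect on one respondent.** I take the Overall score as the average of the seven items, in line with the 1–5 range in Section 11.
- Suppose a user was fitted 4 days ago, wears the device 10 hours a day and averages over the full window: 4 × 10 / 14 = 2.9 h/day. That is the 1-to-4-hour category (score 3) instead of more than 8 hours (score 5).
- The 2-point difference lowers Factor 1 by 2/4 = 0.50 and Overall by 2/7 = 0.29.
- If instead all four items move by one category, Overall moves by 4/7 = 0.57.

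**3. Share of respondents affected.** The documents give no distribution of time since fitting. If fittings accrued evenly over a database of Y years (assumption), the share within the last 14 days is 14 / (365.25 × Y):

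| Y (years) | Share | Per 1000 respondents |
|---|---|---|
| 1 | 3.8% | 38 |
| 3 | 1.3% | 13 |
| 10 | 0.4% | 4 |

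**4. Shift in the pooled mean.** Shift = share × 4/7 × categories moved. With one category on all four items:
- 0.004 × 0.571 = 0.002
- 0.038 × 0.571 = 0.022

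**5. A subgroup of recently launched processors.** The documents give no launch dates. If a model were surveyed m months after launch with even uptake (assumption), the share is 14 / (30.44 × m):
- m = 6: 7.7%, shift 0.077 × 0.571 = 0.04
- m = 3: 15.3%, shift 0.153 × 0.571 = 0.09

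**6. Scale.** With an assumed SD of 0.7 (not in the documents), the 95% half-width of a mean is 1.96 × 0.7 / √n: 0.04 at n = 1000 and 0.19 at n = 50. The pooled shift in step 4 is below the first figure. The subgroup shifts in step 5 are below the second, which applies only if the subgroup has about 50 respondents. Section 11.1 sets that minimum for subgroups 1 to 3 only.

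**The case against.** There is a good case that little is lost here.

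- **Presence is possible, not shown.** Section 9.1 gives neither a sign-up delay nor the timing of the email relative to sign-up. The database is an accumulated list of about 3000 users across several processor families. Section 9.2 allows a month from consent to completion, so some users who are recent at consent will have passed two weeks when they answer. A reader might infer that the invitation list does include very recent users; the documents show only that it can. This stands.
- **The wording may protect the answers.** Item 1 asks about an average day with the present device, and items 5 and 6 also tie the answer to it. A recent user may report only on days of ownership, in which case item 1 carries no error. It is tempting to call such responses invalid, but nothing in the documents says that shorter exposure invalidates them. This stands, and the 4-day example is only an illustration.
- **Uneven distortion across models is an inference.** A reader might conclude that the newest families are hit hardest, because outreach is staged by family. That is plausible, but the documents give no launch dates and no time since fitting by model. The analysis is descriptive, with no planned test between families.
- **An all-user sample is a deliberate choice, and a sensitivity analysis could suffice.** This stands only in part. An all-comers rule suits the non-use and refit percentages. It does not settle which responses fit an instrument with a 14-day window. A sensitivity analysis also needs time since fitting for the current processor, and the item as listed does not clearly provide it.

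**Conclusion.** The gap is real and its likely effect on the pooled result is very small. The documents establish the four two-week items, the absence of any minimum time since fitting, and the lack of any analytic use for the time-of-fitting variable. Following the plan as written would score any respondent whose current processor does not span the recall window, despite the stated interest in long-term use.

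The pooled Overall mean would move by about 0.002 to 0.02 points. This assumes even accrual over 1 to 10 years, all four items moving by one category, and respondents not confining their answers to days of ownership. In a subgroup of recently launched processors the effect could be larger, but the documents do not allow it to be sized, and the figures of 0.04 and 0.09 rest on assumed launch intervals.

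The documents do not support a claim that the primary endpoint is materially biased or that the newer models' results are distorted. The case for acting is that the threshold is the questionnaire's own window and the change is cheap.

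**What to change.** - **Sections 9.1.1 and 11:** compute the Overall, Factor 1, Factor 2 and per-item scores for respondents whose current processor was fitted at least two weeks before survey completion. Counting to completion rather than consent allows for the one-month response period. Report the same scores for all respondents as a sensitivity analysis.
- **Section 9.2.1.1:** word the time-of-fitting item so that it refers to the current processor and can identify less than two weeks.
- **Section 8.2 outcomes:** keep more recent users in the non-use and refit percentages, so those lose nothing.

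The cost is a sentence in each of two sections, a filter, and possibly one reworded survey item, to be settled before fielding. A few recent users would leave the main IOI-HA analysis, and they would still appear in the sensitivity analysis.
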